**HUI sample size calculations:**

Interest is in the difference in change between the 5 age groups of interest. We can look for differences in change between age groups using a one-way analysis of variance where the omnibus test will show if there is a significant difference between any pair of groups.

We use a 5% significance level, power of 80%, and assume a SD=0.22 (from UKCISG) within each group and use the data from UKCISG change in means for each age group (where 0.23 is used for the youngest age group). So, the biggest difference between any pair of groups here is 0.07 units. With these specifications, a sample size of 995 would be required to find a significant difference between at least one pair of age groups.

If the largest difference between the oldest and youngest group was 0.1 with 0.025 difference between all adjacent groups, then a sample size of 470 would be needed to find a significant difference between at least one pair of age groups.

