**SSQ sample size calculations:**

We have no data on the mean and SD for each age group but, using a 5% significance level and power of 80%, and assuming a SD=1.9 if the difference between the oldest and youngest age group is 2 units and there is a 0.5 difference between adjacent groups (so that the youngest group has the MCID in change but the oldest group makes no gain [note that this is not realistic since we know all ages gain]) then a sample size of 95 would be needed to find a significant difference between at least one pair of age groups.

The true difference between age groups is likely to be much smaller. Suppose the youngest age group gains 3 SSQ units for the speech subscale but the oldest age group gains only 2

units. Assume adjacent groups differ by 0.25. Then a sample of 350 participants would be needed to find a significant difference between at least one pair of age groups.

Repeated measures methods, which will be used to analyse the data are more efficient and so it is likely that smaller sample sizes will be needed than stated in the above calculations.

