### 1.3.2.2 Primary Hypothesis and Analysis

The effectiveness of cochlear implantation may vary by adult age group. Effectiveness is defined by the gain in total SSQ or HUI3 scores. As the outcome is likely neutral with respect to implications the hypotheses are presented to look for significant differences rather than to prove equivalence: We are neither worried that older subjects receive less benefit than younger patients, or vice versa since overall benefit is already known for these. However, differences in the benefits may imply revision of rehabilitation and/or counselling for prospective candidates. Thus:

H0: There is no interaction effect between age group and visit on SSQ/HUI3 scores.

H1: There is an interaction effect between age group and visit on SSQ/HUI3 scores.

The proposed method of analysis is to use linear mixed-effects models (LMM). This allows determination of main (fixed) effects (visit, age group) and interaction effects, such as to answer the main objective while utilising all available data and controlling for repeated measures on the same individuals via a random effect for individual.

Tukey pairwise differences will be used to examine differences between age groups (if there is no evidence of an interaction effect) after adjusting for time if there is a significant main effect of age group. If an interaction effect is evident then differences between age groups at each time point can be estimated while controlling appropriately for pairwise testing.

The LMM approach allows the possibility of observing the influence of any continuous or categorical covariates of interest.

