### 1.3.2.3 Secondary Hypotheses

Secondary objectives involve the dichotomisation of HUI and SSQ changes from pre to post where the threshold used is an increase at or above the minimum clinically important difference (>0.03 for HUI and >2 for SSQ). This can be done for baseline to first visit and baseline to second visit (probably not beyond that because of lack of follow-up data).

Bivariate responses will be modelled using mixed-effects logistic regression. Specifically:

H0: There is no interaction effect between age group and visit on the odds of achieving a clinically significant gain in SSQ/HUI3 score.

H1: There is an interaction effect between age group and visit on the odds of achieving a clinically significant gain in SSQ/HUI3 score.

Additional covariates can be included in these models to determine their effects (such as etiology, tinnitus etc).

Alternatively, standard logistic regression models can be used to determine the presence of MCID changes between a pair of time points only (for example baseline to visit 1 or baseline to visit 2).

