### **1.3.7 Presentation of data**

The report will conform to a conventional format with a number of data completeness and population summaries (such as demographics).

For the age groupings, ABS age ranges will be utilised unless sample sizes are too small. In this situation, one or more groups will be combined. While quintiles were of interest the age breakpoints were not useful and not considered further.

For all linear and linear mixed-effects models, estimates of the marginal means and plots of change over time will be presented. P-values for interaction effects and differences between groups (where relevant because of significance or interaction or main effects) will be presented. For logistic models estimated odds ratios and p-values will be presented.

Tables of summaries at each time point will be presented for the overall cohort as well as for those present or absent at a subsequent time point. Tables of cross-tabulations will also be presented.

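### SAP 1.3.2.2 defines effectiveness as gain, but its named age-group follow-ups compare score levels and no adjusted difference in mean gain with an interval is planned

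*SAP*

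**What the plan says.** SAP 1.3.2.2 states the target: "Effectiveness is defined by the gain in total SSQ or HUI3 scores". The null hypothesis of the linear mixed model matches it: "There is no interaction effect between age group and visit on SSQ/HUI3 scores". The sample size section (1.3.1) has the same target: "Interest is in the difference in change between the 5 age groups of interest".

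Two follow-ups are named in 1.3.2.2.

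- **No interaction:** "Tukey pairwise differences will be used to examine differences between age groups (if there is no evidence of an interaction effect"), adjusting for time, when the age main effect is significant.
- **Interaction present:** "If an interaction effect is evident then differences between age groups at each time point can be estimated while controlling appropriately for pairwise testing".

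On reporting, 1.3.7 plans marginal means and plots over time, and then: "P-values for interaction effects and differences between groups (where relevant because of significance or interaction or main effects) will be presented". It names no contrast of change between age groups and no confidence interval. Gain by age otherwise appears in the secondary models of 1.3.2.3, where gain is dichotomised. One option there is that "standard logistic regression models can be used to determine the presence of MCID changes between a pair of time points only".

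**The concern.** The interaction test is an omnibus test. It says that some age groups change differently, but not which, by how much or how precisely. That is the job of the follow-up comparisons, and both of them estimate score levels instead of gain. A level difference at a follow-up visit carries along whatever difference existed before switch-on.

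SAP 1.3.2.2 says that differences in benefit might lead to changes in rehabilitation or counselling. That use needs the size and uncertainty of the difference in gain. If only the named comparisons are reported, an age group that starts lower and gains just as much as the others can look as if it benefits less, and one that starts higher and gains less can look as if it benefits equally.

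The SAP Introduction also says that deviations from the plan need not be reported. Gain contrasts added after the data are seen could then not be told apart from planned ones.

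**Working it through.** **1. What each follow-up estimates.** Let m(i,t) be the mean score in age group i at visit t, with t=0 at baseline, and let the gain be g(i,t) = m(i,t) − m(i,0). Then

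m(i,t) − m(j,t) = [m(i,0) − m(j,0)] + [g(i,t) − g(j,t)].

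The level contrast equals the gain contrast only if the two groups start equal. With baseline, year 1 and year 2 weighted equally and the same gain at both years, the age main effect equals the baseline difference plus 2/3 of the gain difference, so it is not a gain contrast either. The documents give no baseline score by age: SAP Table 1 holds changes, and Table 2 is not split by age.

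**2. The SAP's own sample sizes.** These are one-way ANOVAs on change with 5 equal groups, 5% alpha and 80% power. The noncentrality is N × (variance of the group means) / SD².

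| Scenario (SAP 1.3.1) | Variance of means | SD | N | Noncentrality | Power |
|---|---|---|---|---|---|
| HUI3, means 0.23, 0.21, 0.16, 0.20, 0.18 | 0.000584 | 0.22 | 995 | 12.0 | 80.05% |
| HUI3, range 0.10 in steps of 0.025 | 0.00125 | 0.22 | 470 | 12.1 | 80.3% |
| SSQ, range 2 in steps of 0.5 | 0.5 | 1.9 | 95 | 13.2 | 82.0% |
| SSQ, range 1 in steps of 0.25 | 0.125 | 1.9 | 350 | 12.1 | 80.1% |

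All four stated sizes reproduce exactly. They are planned on differences in change, which confirms gain as the target. They apply to the omnibus test: "Then a sample of 350 participants would be needed to find a significant difference between at least one pair of age groups".

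**3. Precision of the missing contrast.** For youngest against oldest, the half-width is c × SD × √(2/n), with n per group and c the Tukey critical value over the 10 pairs.

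- HUI3, N=470 (n=94): 2.7385 × 0.22 × √(2/94) = 0.088. With the paired-difference SD of 0.182 from Table 2 it is 0.073.
- SSQ, N=350 (n=70): 2.7423 × 1.9 × √(2/70) = 0.88.

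Adjusting over 10 pairs and two follow-up visits that share a baseline raises the critical value to about 2.95 (simulated, normal reference). The half-widths become about 0.095 (0.078 at SD 0.182) and 0.95. The assumed gain differences are 0.10 and 1.0.

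**4. Power of that contrast** (noncentral t, noncentrality d / [SD × √(2/n)]).

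| Case | Noncentrality | Power, pairs | Power, pairs and visits | N for 80%, pairs | N for 80%, pairs and visits |
|---|---|---|---|---|---|
| HUI3 0.10, N=470, SD 0.22 | 3.12 | 64.7% | 56.5% | 620 | 700 |
| HUI3 0.10, N=470, SD 0.182 | 3.77 | 84.8% | 79.2% | 425 | 480 |
| SSQ 1.0, N=350, SD 1.9 | 3.11 | 64.5% | 56.4% | 465 | 520 |

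For the N=995 scenario (largest difference 0.07), power is 67.0% over pairs and 58.7% over pairs and visits.

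**5. Level against gain when baselines differ (illustration only).** The baseline gaps here are assumed. The simulation used 4,000 replicates, a random-intercept model, complete data at three visits, equal groups and the same gain at both years. The total SD is 0.178 for HUI3, from √[(0.188² + 0.168²)/2], and 1.696 for SSQ, from the speech subscale values 1.707 and 1.685. Change SDs are 0.22 and 1.9. Rejection is Tukey-adjusted over pairs.

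| Oldest group at baseline | Level contrast, visit 1: mean (rejects) | Gain contrast: mean (rejects) |
|---|---|---|
| HUI3 0.05 higher | 0.050 (20.2%) | 0.100 (64.8%) |
| HUI3 equal | 0.100 (88.2%) | 0.100 (65.5%) |
| HUI3 0.05 lower | 0.150 (99.9%) | 0.100 (64.0%) |
| SSQ 0.5 higher | 0.504 (16.4%) | 1.00 (64.3%) |
| SSQ equal | 0.999 (76.6%) | 1.00 (64.9%) |
| SSQ 0.5 lower | 1.494 (99.5%) | 1.00 (64.0%) |

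A direct calculation agrees. For HUI3 the level contrast has standard error 0.178 × √(2/94) = 0.026. A mean of 0.05 lies 1.93 standard errors from zero, against a critical value of 2.74, which gives about 21%.

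**The case against.** The primary test is right: the age-by-visit interaction tests differential gain, and no error rate or stated sample size is wrong. The follow-up wording is permissive and does not exclude other contrasts from the same model. Comparisons at each time point include baseline, so a baseline gap would be visible. Marginal means and plots are promised, from which a reader could work out differences in gain, and 1.3.2.3 models clinically significant gain by age. If ages start equal, the planned level contrast is unbiased and more powerful (88% against 66% for HUI3 at SD 0.22; 86% against 85% at SD 0.182).

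Most of this is correct and limits the point. It does not remove it. Subtracting two reported level contrasts gives a point estimate of the gain difference, but no interval and no multiplicity adjustment. The logistic models estimate odds of passing a threshold, not mean gain. In the mixed version the outcome is already a change, so its interaction with visit asks whether age differences vary between visits. Equal starting levels cannot be assumed when the documents give no baseline score by age.

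The figures also have limits. They assume equal groups and complete data, while the SAP expects limited later follow-up and has already combined younger age groups. With, say, 10% of subjects in the youngest and 40% in the oldest group, the HUI3 half-width at N=470 would be near 0.098 instead of 0.088. The SSQ SD is for the speech subscale, although the outcome is the total score, and the HUI3 SDs come from two different samples.

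**Conclusion.** The point holds. The SAP's definition of effectiveness, its hypothesis and its sample sizes all concern gain, while both named follow-ups in the primary model estimate score levels. No adjusted pairwise difference in mean gain with a confidence interval is named anywhere.

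The need for the interval does not rest on any assumed baseline gap. At the SAP's own sizes and SDs, the adjusted half-width is about 0.09 for HUI3 and 0.9 for SSQ, nearly as large as the gain differences planned for. The bias from using level contrasts equals the baseline difference between the age groups, whatever that proves to be. Its size cannot be stated from the documents, and the gaps of 0.05 and 0.5 are illustrations. The interaction test and the stated sample sizes stand as omnibus results.

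**What to change.** In SAP 1.3.2.2, when an interaction is evident, make the main follow-up the pairwise interaction contrasts from the same mixed model: year 1 minus baseline, and year 2 minus baseline, in one age group minus the same change in another. Give simultaneous 95% confidence intervals, adjusted over the 10 pairs and two follow-up visits, with the number of pairs reduced if age groups are combined. When no interaction is evident, report the same intervals descriptively. Keep the per-visit and main-effect comparisons, labelled as level differences and not as differences in effectiveness. List the gain contrasts and their intervals in 1.3.7.

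The cost is a few sentences and one more set of contrasts from a model already fitted. The drawback is power. Adjusted over pairs and visits, the youngest-oldest contrast has about 56% power for both HUI3 (SD 0.22) and SSQ at the stated sizes. The SAP should therefore say that those sizes apply to the omnibus test, that the intervals are the main output, and that a non-significant pair is not evidence of equal gain.

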### 1.3.2.3 Secondary Hypotheses

Secondary objectives involve the dichotomisation of HUI and SSQ changes from pre to post where the threshold used is an increase at or above the minimum clinically important difference (>0.03 for HUI and >2 for SSQ). This can be done for baseline to first visit and baseline to second visit (probably not beyond that because of lack of follow-up data).

Bivariate responses will be modelled using mixed-effects logistic regression. Specifically:

H0: There is no interaction effect between age group and visit on the odds of achieving a clinically significant gain in SSQ/HUI3 score.

H1: There is an interaction effect between age group and visit on the odds of achieving a clinically significant gain in SSQ/HUI3 score.

Additional covariates can be included in these models to determine their effects (such as etiology, tinnitus etc).

Alternatively, standard logistic regression models can be used to determine the presence of MCID changes between a pair of time points only (for example baseline to visit 1 or baseline to visit 2).

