4.1 Preclinical testing

No preclinical testing is required for enrolment of an implanted subject into the registry outside of routine clinical practice.

5 Study Objectives

- To evaluate longitudinal subjective benefit data using validated standardised questionnaires (HUI Mark III and SSQ) for prospectively implanted adult and adolescents using unilateral; bilateral or bimodal configurations of device types.
- To provide statistically valid data to support patient management decisions at the clinical, administrative, reimbursement and regulatory levels locally, nationally and internationally.
- To establish benefits and device functionality for bilateral use over unilateral use for scientific, regulatory and market oriented communications

The hypotheses:

The information gathered shall be used to test the primary hypotheses that implantable hearing solutions improve **the auditory performance** of implant recipients compared to their preimplant condition.

Reported benefits evaluated at 1 year postimplant will remain stable at 2nd and 3rd year postimplant compared to the Baseline evaluation of the preimplant condition.

Severe to profound bilaterally impaired adults and adolescents undergoing bilateral implantation will report a higher level of benefits post implant on self-reported scales, the SSQ and HUI Mark III, compared to those reported by comparable groups of patients implanted unilaterally at the first year follow-up.

Participation in the observational study presents no additional risk to the patient as they are implanted with market released devices and there is no additional burden to the subjects beyond clinical followup.

6 Study Design and End-points

The clinical investigation is designed as a prospective repeated measures longitudinal study with intra-subject controls and inter-group comparisons for device type and configurations across multiple implant

centres cross-culturally using a selection of evaluation tools including clinically standard self-assessment scales, threshold measures, product specific and non-standardised questionnaires for the clinician and implant recipient made available through the electronic platform. Participating clinics are encouraged to collect data as per the evaluation plan outlined. Evaluation tools are provided via the electronic platform.

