## 1 REAL LIFE OUTCOMES VERSUS AGE FOR CI

### 1.1 Overall objectives

- Clinical Evidence Strategy: Healthy Aging
- Pivotal Hypothesis: Are there differences in outcomes with CI for different age ranges, and impact on subject's life
- Primary measures: HUI3, SSQ (complete scales)
- Secondary measures: Changes in HUI3 >0.03, changes in SSQ >2 (i.e. dichotomisation of outcomes), changes in employment status pre and post (1 year, and sustained at 2 years), Medical leave after surgery, employment and other specific questions and listening effort (e.g. from SSQ).
- Age groupings for comparisons:
  - Use ABS-type age groupings 18-34, 35-44, 45-54, 55-64, 65+
  - Note that the younger age groups were combined due to sample size.
- Descriptive statistics of sub populations/ predictors (to be compared: pre and post, pre vs post, by age group, and as potential predictors in regression analyses)
  - Onset of deafness
  - Etiology
  - Hearing loss degree
  - HA use/presence (in the implanted ear at baseline and contralateral ear at baseline and visit 1)
  - Telephone use
  - Presence of tinnitus
  - Presence of dizziness
  - Employment status
  - Whether hearing ability negatively affected work
  - Has ability to do job changed post implant
  - Medical leave (taken and amount)
- Considerations:
  - Bilateral implant summaries were also of interest but were not possible due to small numbers.
  - Some of the above summaries may not be possible due to (subgroup) sample sizes.
  - The questions around employment and leave may not have been captured in a usable form, as such these variables will be explored more carefully, and analyses should be interpreted cautiously.

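### The secondary responder hypothesis tests whether the age gap changes between follow-up visits, not whether the odds of a clinically important gain differ by age

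*SAP*

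**What the plan says.** SAP 1.1 poses the question for the first publication: "Are there differences in outcomes with CI for different age ranges". Dichotomised HUI3 and SSQ changes are listed there as secondary measures.

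SAP 1.3.2.2 fixes what is being compared: "Effectiveness is defined by the gain in total SSQ or HUI3 scores". Its primary hypotheses concern the age-group-by-visit interaction on the scores, in a linear mixed model.

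SAP 1.3.2.3 defines the secondary outcome as a pre-to-post change beyond the threshold (>0.03 for HUI3, >2 for SSQ). On timing it says: "This can be done for baseline to first visit and baseline to second visit", and probably no later. The model is a mixed-effects logistic regression, and the null is: "There is no interaction effect between age group and visit on the odds of achieving a clinically significant gain in SSQ/HUI3 score". As an alternative, "standard logistic regression models can be used to determine the presence of MCID changes between a pair of time points only". No age hypothesis is attached to that alternative.

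Protocol section 5 expects persistence: "Reported benefits evaluated at 1 year postimplant will remain stable at 2nd and 3rd year postimplant".

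**The concern.** The interaction form is right for the primary analysis. There the outcome is the score and baseline is one of the visits, so age-by-visit asks whether the gain differs by age. The secondary outcome already has baseline subtracted. Using the same interaction takes a second difference and asks whether the age gap in responder odds moves between visits 1 and 2.

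Suppose younger recipients respond more often than older ones at year 1, and equally so at year 2. The stated null is then true, however wide the gap. If the protocol's expectation of stable benefit holds within each age group, this is the situation to expect. A non-significant result could then be read as showing that responder odds do not differ by age, which it does not show. SAP 1.3.2.2 says that differences in benefit may lead to revised rehabilitation or counselling, so that misreading would matter.

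**Working it through.** **1. The two interactions side by side.** Let j index age group and t visit.

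- Primary: mean score μ(j,t), t = 0, 1, 2. No interaction means μ(j,t) − μ(j,0) is the same for all j, so gain does not differ by age.
- Secondary: η(j,t) = logit P(gain from baseline > cut-off), t = 1, 2. No interaction means η(j,2) − η(j,1) is the same for all j. This places no restriction on how far η(j,1) differs between age groups.

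Adding baseline as a visit does not help. Everyone would be a non-responder there, which gives complete separation.

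**2. The SAP's sample sizes reproduce.** They are for continuous gain; none is given for the responder analysis. For a one-way ANOVA with five equal groups, λ = N × (variance of group means) / SD².

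- SSQ gains 3, 2.75, 2.5, 2.25, 2: variance = (0.25 + 0.0625 + 0 + 0.0625 + 0.25)/5 = 0.125. λ = 350 × 0.125 / 1.9² = 12.12, power 80.1%. Stated N is 350.
- The other three also reproduce after rounding up to a multiple of five: 92 gives 95 (SSQ), and 467 gives 470 and 994 gives 995 (HUI3).

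**3. SSQ responder rates from those inputs** (SAP 1.3.1: SD 1.9; cut-off 2; N=350, so 70 per group). P = Φ((gain − 2)/1.9), with normal gains assumed.

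| Gain | 3 | 2.75 | 2.5 | 2.25 | 2 |
|---|---|---|---|---|---|
| Responder rate | 0.701 | 0.653 | 0.604 | 0.552 | 0.500 |
| Logit | 0.850 | 0.634 | 0.421 | 0.210 | 0 |
| Weight 70·P(1−P) | 14.68 | 15.85 | 16.75 | 17.31 | 17.50 |

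**4. Three tests on these data, with the same gap at both visits.** λ = Σ w(η − weighted mean)²; Wald test on 4 df, critical value 9.488.

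- Age at visit 1 only: weighted mean 0.405, λ = 2.92 + 0.83 + 0.00 + 0.66 + 2.87 = 7.28, power 56%.
- Age averaged over visits, between-visit correlation 0.6: weights 21.07, 22.63, 23.83, 24.57, 24.83, weighted mean 0.406, λ = 10.38, power 73%.
- Age-by-visit: every η(j,2) − η(j,1) = 0, so λ = 0 and the rejection rate is 5%.

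**5. Range of inputs.** HUI3 uses the SAP's 0.1 gap in steps of 0.025, SD 0.22, cut-off 0.03 and N=470. The youngest-group gain is assumed, because the SAP gives only the gap.

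| Equal gap at both visits | Age averaged, correlation 0.3 / 0.6 / 0.8 | Visit 1 only | Interaction |
|---|---|---|---|
| SSQ, N=350 | 81 / 73 / 67% | 56% | 5.0% |
| HUI3, youngest gain 0.20 | 78 / 70 / 64% | 52% | 5.0% |
| HUI3, youngest gain 0.23 | 75 / 67 / 61% | 49% | 5.0% |
| HUI3, youngest gain 0.25 | 73 / 65 / 59% | 47% | 5.0% |

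Variations, where the interaction stays at 5% throughout:

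- Mean gains at the levels in the Table 2 of SAP 1.3.1 (HUI3 0.09; SSQ 1.18 to 1.80): averaged age test 68–82% and 65–82%.
- Age groups merged to four or three: 62–83% (HUI3) and 70–86% (SSQ).
- Only 117/161 = 73% of N with both visits (one centre's year-1 retention in SAP 4.1.1, used as an illustration): 44–62% and 52–66%.
- HUI3 with the SAP's published age-group means (largest gap 0.07): 30–40% at N=470 and 60–74% at N=995.

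**6. When the gap shrinks.** If it halves by visit 2, the averaged age test rejects 32–51% (HUI3) and 40–54% (SSQ), the interaction 9–17% and 11–19%. The interaction overtakes once about 28–32% of the gap is left at correlation 0.8, 18–21% at 0.6, or 8–10% at 0.3, and when the gap reverses.

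**7. Simulation check.** With 4,000 runs per scenario, correlations 0.3 to 0.7 and an equal gap, the interaction rejected 4.9–5.5%. The averaged age test rejected 72–82% (SSQ) and 63–74% (HUI3, youngest gain 0.25). With an SSQ gap of 2 units (responder rates 85% to 50%, correlation 0.5), the interaction rejected 4.7% and the age test over 99%. These tests are population-averaged. A smaller run of 600 replicates with a random-intercept logistic model gave the same pattern: interaction 4.7–6.7%, age 63–77% (HUI3, youngest gain 0.23) and 68–82% (SSQ).

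**The case against.** The strongest reply is that the age question is covered elsewhere. The primary mixed model tests it correctly on the continuous scores. SAP 1.3.4.4 plans Fisher's exact tests of age group against other categorical variables, drawing on some or all of those in section 1.1, which could include responder status. The single-interval logistic models would naturally carry an age term. SAP 1.3.7 promises odds ratios and p-values for logistic models. SAP 1.3.2.1 sets no pass/fail criterion, so no decision depends on this test. Whether benefit persists equally across ages is also a fair question.

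All of that stands, and it limits the harm. It does not repair the mismatch. The Fisher tests need not include the responder variables, the single-interval models are optional with no named age effect, and the rule on age main effects in SAP 1.3.2.2 is written for the linear mixed model. None of these is the test of a stated responder hypothesis on age.

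Three further points are fair:

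- The powers for the age test rest on planning values and assumptions, including speech-subscale inputs where the outcome is the total SSQ.
- The protocol's stability hypothesis is not age-specific; stability within each age group is an assumption made here.
- SAP 1.3.3.1 leaves a third year possible. The interaction would then cover changes across three visits, with the same mismatch.

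**Conclusion.** The concern holds: the secondary hypothesis is wrong as written for the question it serves. That conclusion follows from the definition of the outcome and needs no modelling assumption. The 5% rejection rate under a lasting gap follows by construction.

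The size of the contrast does depend on assumptions: normal gains, equal groups, complete data at both visits, between-visit correlation 0.3–0.8 and a HUI3 youngest-group gain of 0.20–0.25. On those terms the averaged age test rejects about 58–78% for HUI3 and 67–82% for SSQ. It falls to 30–40% for HUI3 at N=470 with the published age-group means. The interaction is the more powerful test only if most of the gap disappears by year 2 or reverses.

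The consequence is a risk to interpretation, not to a decision rule. This should be fixed before the analysis is reported.

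**What to change.** In SAP 1.3.2.3, restate the null as no difference between age groups in the odds of a clinically significant gain, and the alternative as a difference. Test it in the same mixed logistic model with a joint test of the age-group effect, on df equal to the number of age groups minus one (4 with five groups; fewer if groups are combined under SAP 1.3.7).

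Pre-state one contrast. Either the effect averaged over visits 1 and 2 (sum-to-zero coding or marginal contrasts if the interaction is retained) or visit 1 alone would serve. Keep age-by-visit as a supplementary test of whether the age effect persists from year 1 to year 2. If the single-interval logistic models are used instead, name the age-group term as the tested effect.

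The cost is SAP wording and a line on coding. No new data and no different model are needed.
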